9.2 Deaths, Serious Adverse Events and other Significant Adverse Events

All the serious adverse events will be recorded. The relationship with study drug will be summarized

9.3 Pregnancies

Pregnancy reports will be sent to Biosidus S.A. so as to be included in the safety database. This requirement includes the normal pregnancies without AEs.

A pregnancy follow-up must be made in order to determine pregnancy results, including spontaneous or voluntary interruption, the birth details, the presence or absence of any birth defect, congenital anomalies or complications in the mother or in the newborn. The pregnancy follow-up report should be registered in the specific eCRF.

9.4 Clinical Laboratory Evaluations

For the assessment of safety, the determination of complete laboratory parameters will be determined in the baseline visit, and during visits weeks 12 and 24, or at the end of the study, in which the following parameters will be tested:

- Liver function tests,
- Glycemia, lipid profile (HDL, LDL, and triglycerides),
- Ionogram, calcium, phosphorus, urea, and creatinine, and
- Sideremia (serum iron), transferrin and its saturation, and ferritin

The values of these parameters will be evaluated and summarizes by treatment group as if within the normal range or out of range. In this case, clinical significance will be provided, as clinically significant or not clinically significant. .

10 Quality Control

The investigator, study coordinator, or other study staff, duly trained and appointed, performed the data entry in the center. The eCRFs were completed for each recruited patient according to the patient source data at each visit.

Patients were not identified by name. An appropriate coded identification was used; so that the patient could not be identified. The center investigator kept separately a form with the patient's name, the non-identifiable initials and the patient's address (i.e., an identification patient form).

The center investigator checked that each CRF was duly completed at each visit, and the clinical studies monitor confronted them with the source documents. The monitor and staff from Data Management department (DM) monitored each entry.

Integrity and internal consistency of data introduced in the study database were controlled during the monitor visit, versus the patient's clinical history as source document. Deviations from these pre-defined and computerized validations arouse incoherencies in the database that were solved using the data correction form.

There are 2 mainly type of discrepancies:

- Automatic discrepancies, automatically generated during the data entry or following the data logical execution.
- Manual discrepancies, which a system user may generate at any time.

The investigator and his/her team were responsible for solving any data discrepancy in time and shape. Study monitors carried out the follow-up to confirm that the discrepancies had been solved.

The population to be used in a table or figure will be explicitly set at the start of a block of code that computes the output.

11 Technical Details

The randomization system was defined in the electronic data collection system. provided by the company Semicrol® S.L., Santander, Spain.

The Sponsor chose an electronic data capture (EDC) system (electronic CRF). The company Semicrol® (Santander, Spain) provided the service. The Sponsor granted Access to the system to all the PIs and to all the staff selected.

Statistical analysis will be performed with SPSS (Statistical Package for Social Sciences) software² or equivalent, such as the R Core Team Program (2020)³

12 Summary of Changes to the Protocol

Two general amendments, that were applicable to all the participating centers, were made.

Amendment #1 added two additional dosage forms of the study product (pre-filled syringes x 1000 and 3000 IU) and introduced some changes at the requirement of one of the Ethics Committees, which had been extended to all the centers. These modifications included a change regarding the Pregnancy tests in urine by the HCG beta sub-unit determination in blood, additional information about statistical tests and the descriptive statistics to be used, among others, were also included.

Amendment #2 added Paraguay and Uruguay as countries that might take part of the study, potentially.

13 References

¹ Schulz KF, Altman DG, Moher D; CONSORT Group. CONSORT 2010 statement: updated guidelines for reporting parallel group randomized trials. *Ann Intern Med.* 2010 Jun 1;152(11):726-32. doi: 10.7326/0003-4819-152-11-201006010-00232. Epub 2010 Mar 24. PMID: 20335313.

² IBM SPSS version 25.0

³ R Core Team (2020). R: A language and environment for statistical computing. R Foundation for Statistical Computing, Vienna, Austria. URL <https://www.R-project.org/>.

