14.2.7 Full laboratory tests

A full laboratory test will be performed at the baseline visit (week - 1) and at the week 12 and week 24 visits or at study completion visit and all clinically relevant data will be recorded in the source documents of the patient and in the individual case record form (ICRF). Samples for full local laboratory test will consist of:

- Complete hemogram with reticulocyte (through flow cytometry or hematologic counter) and platelet count.
- Hepatogram,
- Glycemia, lipid profile (HDL, LDL and triglycerides)

- Ionogram, calcium, phosphorus, urea and creatinine,
- Serum iron, transferrin, transferrin saturation, and ferritin
- Beta subunit of chorionic gonadotropin only in women of childbearing potential
- Serum/ plasma sample for antibodies and hepcidin dosage (the sample will be collected and stored frozen at - 20° C for further analysis)

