4.2 Selection (Inclusion-Exclusion) Criteria

INCLUSION CRITERIA

Patients must meet all of the following inclusion criteria to be eligible for the study:

- 1) Patients between 18 and 85 years of age of both sexes.
- 2) IRC defined by the glomerular filtration rate through the MDRD formula that is ≥ 15 ml/ min and < 60 ml/ min by 1.73 m².
- 3) Anemia with indication of treatment and Hb lower than 10.5 g/ dl and greater than 7.5 g/ dl.
- 4) Patients who have both the will and the capacity to give informed consent in writing.
- 5) Women with at least 2 years of menopause or surgically sterile 6 months ago or of childbearing potential that have a negative pregnancy test during the baseline visit and are willing to receive an effective birth control method (diaphragm or prophylactic associated with a spermicide since at least 21 days before the first treatment; or intrauterine device in place for at least 3 months before the first dose of epoetin alfa: or hormonal birth control method, in pills, patch or implant, initiated at least 3 months before the first treatment).

EXCLUSION CRITERIA

Any of the following criteria exclude the patient from participating in the study:

- 1) Patient with scheduled entry to dialysis or kidney transplant in the next 6 months.
- 2) Transferrin saturation $< 20\%$.

- 3) Cause of renal failure (as the secondary ones to autoimmune diseases) that in the opinion of the physician may affect the normal development of the Protocol.
- 4) Active bleeding or history of hemorrhage that has caused significant decrease of hematocrits in the last 30 days.
- 5) Uncontrolled hypertension (≥ 160 mm Hg systolic pressure and/ or ≥ 100 mm Hg diastolic pressure with anti - hypertensive treatment).
- 6) Anemia due to another cause other than the kidney disease.
- 7) Transfusion in the last 3 months before the baseline or screening visit.
- 8) Treatment with an erythropoiesis stimulating agent in the 3 months prior to the baseline or screening visit.
- 9) Increased risk of thromboembolic disease: Previous history of arterial thromboembolism (CVA, TIA, Acute Coronary Syndrome or other) in the last 6 months or venous thrombosis in the last twelve months prior to the baseline visit; surgery in the last month prior to the baseline visit; prolonged standstill or orthopedic surgery scheduled in the next 6 months or any other factor which in the opinion of the investigator may increase the risk of thromboembolism in the patient.

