6.4 Interim Analyses

A first interim analysis will be performed after the last study patient completes the week 12 visit and the database is clean. This analysis will produce all the efficacy and safety results at week 12.

7 Summary of Study Data

All data will be listed, taking into account site, subject, treatment, and visit number. All summary tables will be structured with a column for each treatment and will be annotated with the total population size relevant to that table, including any missing observations

Descriptive statistics:

Continuous variables will be summarized using descriptive statistics: N, mean, standard deviation, median, minimum and maximum.

Categorical variables will be presented using frequencies and percentages

Inferential statistics

Inferential statistics will be performed through intergroup analysis using ANCOVA covariance analysis comparing each treatment group (patients treated with HEMAX PFS versus those treated with EPREX/ ERYPO®) or the statistical “t” Student test for independent samples considering 5% significance level can be used. An additional intragroup analysis evaluating the variations in hemoglobin (increase from baseline to the average of the visits between weeks 8 and 12) adjusted for the baseline value, using a significance level of 5% will be calculated.

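### SAP 9.4 summarises safety laboratory values only as in or out of range, which is insensitive to further worsening of analytes already abnormal at baseline, and it omits the hemogram

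*SAP*

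**What the plan says.** SAP 9.4 is the only place that gives a summary specific to the safety laboratory tests. Values from baseline, week 12 and week 24 (or study end) are "summarizes by treatment group as if within the normal range or out of range". For those out of range, "In this case, clinical significance will be provided, as clinically significant or not clinically significant". No criteria are given for that label.

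The 9.4 list covers liver tests, glycemia and lipids, iron parameters, and a line reading "Ionogram, calcium, phosphorus, urea, and creatinine, and". No hemogram appears. Protocol 14.2.7 puts first in the full panel for weeks -1, 12 and 24: "Complete hemogram with reticulocyte (through flow cytometry or hematologic counter) and platelet count". The schedule table in SAP 4.4 also names the hemogram as a component of the complete laboratory test.

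On the population, SAP 4.2 requires "IRC defined by the glomerular filtration rate through the MDRD formula that is ≥ 15 ml/ min and < 60 ml/ min" per 1.73 m².

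Two general rules in SAP 7 also bear on the point: "Continuous variables will be summarized using descriptive statistics: N, mean, standard deviation, median, minimum and maximum", and "All data will be listed, taking into account site, subject, treatment, and visit number". SAP 9.1 and Protocol 16.6 say that complete laboratory data at baseline, week 12 and week 24 will be discussed, without giving a method.

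**The concern.** A two-category summary registers a change only when a value crosses a reference limit. In a trial restricted to chronic kidney disease, the analytes that track renal function are the ones most likely to lie beyond that limit at entry. For such a patient, stability and marked deterioration give the same table entry.

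The stake is the descriptive safety comparison of the two products. Safety is one of the two primary objectives. That objective is worded as incidence of adverse events and reactions, but SAP 3.2.3 and 9.1 list complete laboratory data as a safety focus. If one arm's renal chemistry drifted upwards more than the other's, the only table specified for it would respond weakly.

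The hemogram gap is separate. Hemoglobin is fully covered as the efficacy variable, but no specific analysis is named for platelets, reticulocytes or leucocytes, although the hemogram is collected.

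**Working it through.** The documents give no figure on this point, so there is nothing to reproduce. The check has three parts.

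**1. How far creatinine can move inside the out-of-range category.**

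Inputs: the GFR limits of 15 and 60 come from SAP 4.2. The documents name MDRD but print no equation, so the 175-constant form is assumed, with age 65 as an example.

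Formula: creatinine = (GFR / (175 × f × age^-0.203))^(-1/1.154), with f = 1 for men and 0.742 for women. At age 65, age^-0.203 ≈ 0.4285, so for men 175 × 0.4285 ≈ 75.0.

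- Man, GFR 30: (30/75.0)^(-0.8666) ≈ 2.21 mg/dl.
- Man, GFR 15: (15/75.0)^(-0.8666) ≈ 4.03 mg/dl.

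| GFR | Man, 65 | Woman, 65 |
|---|---|---|
| 60 | 1.21 | 0.94 |
| 45 | 1.56 | 1.20 |
| 30 | 2.21 | 1.71 |
| 15 | 4.03 | 3.11 |

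Halving GFR multiplies creatinine by 2^(1/1.154) ≈ 1.82 at any age and in either sex. The man who goes from 2.21 to 4.03 would be expected to be out of range at both visits, so his category does not change.

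**2. How many patients could still show a new out-of-range value.**

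Inputs: 23 and 20 patients enrolled (SAP 5). The share p already out of range at baseline is not in the documents and is varied as an assumption.

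Formula: patients still in range at baseline = n × (1 − p). This is the most that could move from in range to out of range.

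| Assumed p | HEMAX PFS, n = 23 | EPREX/ERYPO, n = 20 |
|---|---|---|
| 0.5 | 11.5 | 10 |
| 0.8 | 4.6 | 4 |
| 0.9 | 2.3 | 2 |
| 0.95 | 1.2 | 1 |
| 1 | 0 | 0 |

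The category table is wholly uninformative about worsening only at p = 1. At p = 0.9 about two patients per arm could register a change.

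**3. Panel against analysis list.**

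| Source | Hemogram |
|---|---|
| Protocol 14.2.7 | Listed first, with reticulocytes and platelets |
| SAP 4.4 | Named in the complete laboratory test |
| SAP 9.4 | Not listed |

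The remaining groups in 9.4 match the Protocol panel (liver tests; glycemia and lipids; ionogram, calcium, phosphorus, urea and creatinine; iron). The missing hemogram therefore looks like an omission. Nothing in the SAP explains it.

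**The case against.** The strongest reply is that the information is not lost. SAP 7 promises mean, SD, median and range for continuous variables and a listing of all data by subject and visit. SAP 9.1 says the laboratory data will be discussed. Protocol 15 makes an abnormal finding an adverse event if it leads to withdrawal, accompanies a serious event, comes with signs or symptoms, or is judged clinically relevant. The significance label can also change between visits when the range category does not.

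This stands to the extent that a reader might infer from 9.4 that worsening could not be seen at all. The documents do not support that reading. The reply does not close the gap, though. SAP 7 names no change from baseline, and the SAP does not say whether its general rule or the specific one in 9.4 applies to these values. A rise of 4.03 − 2.21 = 1.82 mg/dl in one patient shifts an arm mean by only 1.82/23 ≈ 0.08 or 1.82/20 ≈ 0.09. The maximum need not move either, since entry is allowed at GFR 15.

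Other strong readings also fail:

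- **Nearly everyone out of range at baseline.** The documents give no reference limits, and testing is at local laboratories. Patients near GFR 60 may well be in range; the woman in the table has about 0.94 mg/dl.
- **The same argument for potassium or platelets.** Nothing shows that potassium is commonly abnormal at entry, and an analyte that starts in range does register when it leaves it. Platelets are not on the 9.4 list, so the in/out rule does not reach them.
- **An unblinded investigator as the only safeguard.** The trial is open-label, but 9.4 does not say who assigns clinical significance.
- **Hemogram absent from the SAP.** It is in the 4.4 schedule, and hemoglobin is analysed throughout. What is missing is its place in 9.4.

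**Conclusion.** The point holds in a limited form. The in/out summary in SAP 9.4 is insensitive to worsening of analytes already abnormal at baseline, notably creatinine and urea. No change-from-baseline or shift summary is specified anywhere for laboratory values. The 9.4 list omits a hemogram that the Protocol and the SAP's own schedule include.

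The size depends on the unknown share out of range at baseline. At an assumed 50% about half the patients could still register a new abnormality; at 90%, about two per arm. The creatinine example rests on the 175-constant MDRD equation and on the expectation that about 2.2 mg/dl exceeds a local upper limit for men. The urea statement is reasoning by analogy and has no calculation behind it.

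This is a reporting weakness in descriptive safety tables. It does not touch the primary efficacy comparison, and it does not imply that a safety signal has been missed. It is worth correcting because the data exist and the correction is cheap.

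**What to change.** Amend SAP 9.4 as follows, all by treatment arm:

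1. For each parameter, and for eGFR by the MDRD version used for eligibility, report the value at baseline and the value and change from own baseline at weeks 12 and 24, with N, mean, SD, median, minimum and maximum.
2. Add shift tables from baseline category to follow-up category.
3. Add platelets, leucocytes and reticulocytes.
4. Keep the in/out and clinical-significance flags as supplements, and state who assigns significance and by what criteria.
5. State that the SAP 7 statistics apply to these values in addition to the flags.

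If the sponsor wants a count of patients with marked worsening, the threshold is for the sponsor to prespecify; the documents imply none. Since SAP 5 reports that an interim analysis has taken place, tables added now should be labelled as added after it.

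The cost is a few more descriptive tables. No new tests, visits or patients are needed, since eGFR follows from creatinine, age and sex under the equation assumed above. With 23 and 20 patients these tables will describe rather than test, and more tables bring more chance differences, so they should be presented without significance claims.
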